10.2.3 Adverse event of special interest and safety topics of interest

AESI (in the opinion of the investigator) will be flagged in the study database. In addition, an AESI is considered to have occurred if any TEAE which meets the Hy's Law criteria, defined as $\geq 3x$ upper limit of normal (ULN) alanine aminotransferase (ALT) or aspartate aminotransferase (AST) with coexisting $\geq 2x$ ULN total bilirubin in the absence of $\geq 2x$ ULN alkaline phosphatase (ALP), with no alternative explanation for the biochemical abnormality. Hy's law criteria will be summarized as described in [Section 10.3](#).

TEAEs are defined as Safety Topics of Interest and reported as follows:

1. Infections (serious, opportunistic, fungal and TB)
 - Serious infections will be identified based on MedDRA classification (SOC “Infections and infestations”). (Although not required by the ‘Safety Topics of Interest for the Bimekizumab Program’ document, a separate table will be created for these events.)
 - Fungal infections will be summarized in a stand-alone table. The table will include all TEAEs (serious and non-serious) which code into the High Level Group Term “Fungal infectious disorders”.
 - Opportunistic infections (including TB) will be summarized in a stand-alone table. The table will include all opportunistic infection TEAEs identified using UCB-defined search criteria which were adjudicated as opportunistic infections. The process for identifying opportunistic infections is outlined in [Section 12.3](#).
2. Malignancies
 - One table will be based on the criteria standardized MedDRA query (SMQ)=“Malignant or unspecified tumours (SMQ)”.
 - One table will be based on the criteria SMQ=“Malignant tumours (SMQ)”.

SMQ search should include all TEAEs which code to a PT included in the Scope=Narrow group within each SMQ.

Note that the events included in the “Malignancies” table will be a subset of the events included in the “Malignancies (including unspecified)” table. While the “Malignant tumours (SMQ)” is most relevant, “Malignant or unspecified tumours (SMQ)” must be reviewed for potential malignancies.

The output tables will include 2 different overall incidence rows:

- The first overall incidence row will summarize “Any Malignancy” and this row will summarize the incidence of all AEs flagged for inclusion in the table (using the appropriate SMQ depending on the table), regardless of the HLT it codes to.
- The second overall incidence row will summarize “Any Malignancy excluding non melanotic skin cancers HLT” and this row will summarize the incidence of AEs flagged for inclusion in the table (using the appropriate SMQ depending on the table), excluding those which code to an HLT of “skin neoplasms malignant and unspecified (excl melanoma)”.

3. MACE

Major adverse cardiac events will be presented in a table. The classification of an event as MACE is determined by an external cardiovascular event adjudication committee.

A separate table and listing will present adjudicated cardiovascular events by type. For each cardiovascular event type (24 in total), the individual PTs which fall within each event type will be summarized.

Extended MACE events will be presented in a separate table and listing. All events which are classified by the adjudication committee as any of the event types in [Table 10–3](#) will be considered an extended MACE event.

Table 10–3: Extended MACE types

Event Type Code	Event Type
1	Non-Fatal Myocardial Infarction (MI)
2	Non-Fatal Stroke: hemorrhagic
3	Non-Fatal Stroke: ischemic
4	Non-Fatal Stroke: embolic
5	Non-Fatal Stroke: undeterminable
6	Hospitalization or ER for Unstable Angina with urgent revascularization
8	Hospitalization for Heart Failure

Table 10–3: Extended MACE types

Event Type Code	Event Type
10	Coronary Revascularization Procedures (e.g. percutaneous coronary intervention, coronary artery bypass grafting)
11	Urgent Revascularization Procedures (i.e. due to symptoms of brain ischemia or pending infarction)
18	Death due to Myocardial Infarction (MI)
19	Death due to Stroke
20	Sudden Cardiac Death
21	Other CV Death (e.g. heart failure, pulmonary embolism, cardiovascular procedure-related)
22	Cardiovascular Undetermined Cause of Death (i.e. cause of death unknown)

CV=cardiovascular; ER=emergency room; MI=myocardial infarction.

Additionally, a listing of all events identified for potential review by the cardiovascular event adjudication committee will be produced. This listing will indicate whether each event was escalated to the committee for formal review/adjudication.

4. Neutropenia

A table will be created based on the following PTs (regardless of seriousness):

- Autoimmune neutropenia
- Band neutrophil count decreased
- Cyclic neutropenia
- Febrile neutropenia
- Idiopathic neutropenia
- Neutropenia
- Neutropenic infection
- Neutropenic sepsis
- Neutrophil count decreased

5. Suicidal Ideation and Behavior

An external neuropsychiatric adjudication committee will evaluate potential neuropsychiatric events and determine whether any of those events were associated with suicidal ideation and

behavior (SIB). A table and listing for SIB events as determined by the adjudication committee will be produced.

A separate table will present the adjudicated neuropsychiatric events by type. For each neuropsychiatric event type (6 in total), the individual PTs which fall within each event type will be summarized. The table will include events adjudicated as SIB and events adjudicated as non-suicidal (note that the event type ‘Suicidal ideation’ may be classified as either SIB or non-suicidal). The neuropsychiatric event types/codes are as follows:

- Event type code 1: Suicidal events/completed suicide
- Event type code 2: Suicide attempt
- Event type code 3: Preparatory acts toward imminent suicidal behavior
- Event type code 4: Suicidal ideation
- Event type code 7: Nonsuicidal Self-injurious behavior
- Event type code 8: Nonsuicidal Other

Additionally, a listing of all events identified for potential review by the neuropsychiatric adjudication committee will be produced. This listing will indicate whether each event was escalated to the committee for formal review/adjudication. A separate listing will also be produced to summarize the adjudicated results of all events escalated to the full committee.

6. Inflammatory bowel disease

An external IBD adjudication committee will evaluate potential IBD events and will classify these according to the event type in [Table 10-4](#).

Table 10-4: Inflammatory bowel disease types

Event Type Code	Event Type
1	Possible IBD – Crohn’s Disease
2	Probable IBD – Crohn’s Disease
3	Definite IBD – Crohn’s Disease
4	Possible IBD – Ulcerative Colitis
5	Probable IBD – Ulcerative Colitis
6	Definite IBD - Ulcerative Colitis
7	Possible IBD - Unclassified

Table 10–4: Inflammatory bowel disease types

Event Type Code	Event Type
8	Probable IBD - Unclassified
9	Definite IBD - Unclassified
10	Symptoms not consistent with IBD
11	Possible IBD – Microscopic Colitis
12	Probable IBD – Microscopic Colitis
13	Definite IBD - Microscopic Colitis
14	Possible IBD – no further differentiation possible
15	Probable IBD – no further differentiation possible
16	Definite IBD - no further differentiation possible
99	Not enough information to adjudicate

IBD=inflammatory bowel disease.

A table for adjudicated IBD events (event type codes 1, 2, 3, 4, 5, 6, 7, 8, 9, 11, 12, 13, 14, 15 and 16) as determined by the adjudication committee will be produced. It will summarize events determined by the adjudication committee as definite IBD (event type codes 3, 6, 9, 13, and 16), probable IBD (event type codes 2, 5, 8, 12, and 15) and possible IBD (event type codes 1, 4, 7, 11, and 14). Definite and probable IBD events will also be aggregated and summarized in the same table. This table will be stratified by subjects with or without a previous medical history of IBD. Previous medical history of IBD will be determined using the information recorded on the Extra-Articular Assessment form at Screening in AS0008 ("Does subject have a history of IBD?"").

A separate table will present the adjudicated gastrointestinal events by type. For each gastrointestinal event type (event type codes 1 through 16 and 99; 17 in total), the individual PTs which fall within each event type will be summarized. This table will include events determined by the adjudication committee as definite IBD, probable IBD, and possible IBD. It will also include events determined as 'Symptoms not consistent with IBD' (event type code 10) and 'Not enough information to adjudicate' (event type code 99). A corresponding listing by event type will also be presented.

A listing of all events identified for potential review by the IBD adjudication committee will be presented. This listing will indicate whether each event was escalated to the committee for formal review and adjudication.

Finally, a separate listing will be presented showing individual diagnostic criteria met for each adjudicated IBD event.

7. Hypersensitivity (including Anaphylaxis)

A separate table will be prepared based on the MedDRA anaphylaxis algorithm ([Section 12.4](#)) for acute anaphylactic events (reported on the same day as when an injection was administered or one day after). An AE glossary table will also be produced to summarize the MedDRA coding for these events. The glossary table will include the following fields: reported term, PT, LLT, HLT, and SOC.

A separate table will be prepared to summarize hypersensitivity events, identified using the SMQ “Hypersensitivity (SMQ)”. All TEAEs which code to a PT included in the Scope=Narrow search will be included in this table. An AE glossary table will also be produced to summarize the MedDRA coding for these events. The glossary table will include the following fields: reported term, PT, LLT, HLT, and SOC.

Injection site reactions will be evaluated based on the “any TEAE” table by looking under the following HLTs: “Administration site reactions NEC” and “Injection site reactions”.

8. Hepatic events and DILI

A table for hepatic events will be created based on the SMQ of “Drug related hepatic disorders - comprehensive search (SMQ)”. However, these 2 sub-SMQs are to be excluded: “Liver neoplasms, benign (incl cysts and polyps) (SMQ)” and “Liver neoplasms, malignant and unspecified (SMQ)”. For each of the above SMQs, all TEAEs will be included which code to a PT included in the Scope=Broad and/or Scope=Narrow.

Note that all AEs meeting the above criteria will be included, and will not be limited to events that the investigator determined to be related to study drug.

The incidence of AEs defined as Safety Topics of Interest will be summarized by MedDRA SOC, HLT, and PT (apart from the summary of each cardiovascular event type which will use PT only). The EAIR with associated 95% CI and the EAER will be included in the summary tables.

10.2.4 Impact of COVID-19

In order to assess the impact of the COVID-19 global pandemic on the primary safety endpoint of incidence of TEAEs and serious TEAEs, additional listings and summaries will be presented.

For reporting purposes AEs will be assigned to ‘Prior to COVID-19 pandemic’, ‘During the COVID-19 pandemic’ or ‘Post the COVID-19 pandemic’ based on the following:

- If the date of AE onset (based on imputed start date) is prior to 11 March 2020 the AE will be assigned as ‘Prior to COVID-19 pandemic’
- If the date of AE onset (based on imputed start date) is on or after 11 March 2020 the AE will be assigned as ‘During the COVID-19 pandemic’
 - The date of 11 March 2020 is chosen as the date the World Health Organization declared COVID-19 as a pandemic.

- If the date of AE onset (based on imputed start date) is after the date on which the World Health Organization declares the end of the COVID-19 pandemic the AE will be assigned as ‘Post the COVID-19 pandemic’
 - If the date of the end of the COVID-19 pandemic is on or after the date of last subject, last visit, the ‘Post the COVID-19 pandemic’ phase will not apply.

The following categories of TEAE will be summarized by MedDRA SOC, HLT and PT, including EAIR and EAER:

- All TEAEs by time of onset relative to COVID-19 pandemic (‘Prior to COVID-19 pandemic’, ‘During the COVID-19 pandemic’ and ‘Post the COVID-19 pandemic’)
- All serious TEAEs by time of onset relative to COVID-19 pandemic (‘Prior to COVID-19 pandemic’, ‘During the COVID-19 pandemic’ and ‘Post the COVID-19 pandemic’)
- All COVID-19 related TEAEs by treatment at completion of AS0008 and overall
 - COVID-19 related TEAEs will be identified based on the verbatim term including the text string ‘COVID’. These will include confirmed or suspected COVID-19 infections.

TEAEs leading to study discontinuation and/or permanent withdrawal of study medication will be summarized by MedDRA SOC, HLT, and PT, and by time of onset relative to COVID-19 pandemic (‘Prior to COVID-19 pandemic’, ‘During the COVID-19 pandemic’ and ‘Post the COVID-19 pandemic’).

A separate listing of all COVID-19 related AEs will be presented, where COVID-related AEs are identified as described above. In addition, the time of onset of each AE relative to the COVID-19 pandemic will be flagged in all AE listings.

For all listings and summaries described above the ‘Post the COVID-19 pandemic’ phase will be omitted if the date of the end of the COVID-19 pandemic is on or after the date of last subject, last visit.

For the purpose of calculating EAIR and EAER prior to, during, and post the COVID-19 pandemic the rules in [Table 10-5](#) will be applied in the calculation of exposure time at risk. An individual subject may therefore be counted in the denominator for all applicable periods (‘Prior to COVID-19 pandemic’, ‘During the COVID-19 pandemic’ and ‘Post the COVID-19 pandemic’), dependent on whether the subject is still considered at risk at the time of the start date for each successive period. The time at risk will be calculated separately for each period in which the subject is counted. Subjects who are no longer in the exposure time at risk period ([Table 10-2](#)) on the start date of a specific COVID-19 reporting period will not be counted in the denominator for that period ie, a subject who has withdrawn from the study prior to 11 March 2020 and is no longer at risk will not be included in the denominator for the ‘During the COVID-19 pandemic’ or the ‘Post the COVID-19’ pandemic periods.

Table 10-5: Calculation of exposure time at risk in relation to COVID-19

Study Period	Start Date	End Date	Duration of Exposure
Prior to COVID-19 pandemic	First dose of BKZ 160mg in AS0009	10MAR2020	
This period is applicable for all subjects in the SS. The following rules will be applied:
 
For subjects who did not discontinue medication in the 'Prior to COVID-19 pandemic' phase (ie, where the last dose of BKZ 160mg is on or after 11MAR2020):
 
(End date – start date + 1)
 
For subjects who discontinued medication in the 'Prior to COVID-19 pandemic' phase (ie, where the last dose of BKZ 160mg is prior to 11MAR2020):
 
If the following is true:
 
Minimum of (Last dose date in AS0009 + 140^a) and (Date of last clinical contact^b) is \geq11MAR2020
 
Then the duration of exposure will be calculated as follows:
 
(End date – start date + 1)
 
Else duration of exposure will be calculated as follows:
 
Minimum of [(Last dose date in AS0009 – First dose date in AS0009 + 140^a) +1] and (Date of last clinical contact^b – First dose date in AS0009 + 1)
 
For subjects that died on or before 10MAR2020:
 
Date of death – Start date + 1
 
Note: If the date of death is later than 140 days following the last dose of BKZ, this rule does not apply.

During the COVID-19 pandemic	11MAR2020	Date of end of pandemic	
This period is applicable for all subjects in the SS who are still considered at risk on the 11MAR2020 (ie, those for whom either dosing is continuing or for whom the 140 day SFU period after last dose has not been completed [in the case of premature treatment discontinuation]). The following rules will be applied:
 
For subjects who did not discontinue medication in the 'During the COVID-19 pandemic' phase (ie, where the last dose of BKZ 160mg is on or after the date of the end of the pandemic +1): (End date – start date + 1)
 
For subjects who discontinued medication in the 'Prior to COVID-19 pandemic' phase (ie, where the last dose of BKZ 160mg is prior to 11MAR2020): If the following is true: Minimum of (Last dose date in AS0009 + 140^a) and (Date of last clinical contact^b) is \geq11MAR2020 Then the duration of exposure will be calculated as follows: Minimum of [(Last dose date in AS0009 – 11MAR2020 + 140^a) +1] and (Date of last clinical contact^b – 11MAR2020 + 1) For subjects that died in the 'During the COVID-19 pandemic' phase: Date of death – 11MAR2020 + 1 Note: If the date of death is later than 140 days following the last dose of BKZ, this rule does not apply.
 
For subjects who discontinued medication in the 'During the COVID-19 pandemic' phase (ie, where the last dose of BKZ 160mg is on or after 11MAR2020 and on or before the date of the end of the pandemic): If the following is true: Minimum of (Last dose date in AS0009 + 140^a) and (Date of last clinical contact^b) is $>$ the date of the end of the pandemic Then the duration of exposure will be calculated as follows: (Date of end of pandemic – 11MAR2020 + 1) Else duration of exposure will be calculated as follows:

------------------------------	-----------	-------------------------	---

Table 10-5: Calculation of exposure time at risk in relation to COVID-19

Study Period	Start Date	End Date	Duration of Exposure
			
Minimum of [(Last dose date in AS0009 – 11MAR2020 + 140^a) +1] and (Date of last clinical contact^b – 11MAR2020 + 1)
 
For subjects that died in the ‘During the COVID-19 pandemic’ phase:
 
Date of death – 11MAR2020 + 1
 
Note: If the date of death is later than 140 days following the last dose of BKZ, this rule does not apply.

This document cannot be used to support any marketing authorization application and any extensions or variations thereof.
PUBLIC COPY

Table 10-5: Calculation of exposure time at risk in relation to COVID-19

Study Period	Start Date	End Date	Duration of Exposure
Post the COVID-19 pandemic	Date of end of pandemic + 1	Last dose of BKZ 160mg in AS0009	
This period is applicable for all subjects in the SS who are still considered at risk on the day after the end date of the pandemic (ie, those for whom either dosing is continuing or for whom the 140 day SFU period after last dose has not been completed [in the case of premature treatment discontinuation]). The following rules will be applied:
 
For subjects who did not discontinue medication in the ‘During the COVID-19 pandemic’ phase (ie, where the last dose of BKZ 160mg is on or after the date of the end of pandemic +1):
 
Minimum of [(Last dose date in AS0009 – (date of the end of pandemic +1) + 140^a) + 1] and (Date of last clinical contact^b – (date of the end of pandemic +1) + 1)
 
For subjects that died:
 
Date of death – (date of the end of pandemic +1) + 1.
 
Note: If the date of death is later than 140 days following the last dose of BKZ, this rule does not apply.
 
For subjects who discontinued medication in the ‘During the COVID-19 pandemic’ phase (ie, where the last dose of BKZ 160mg is on or before the date of the end of pandemic):
 
If the following is true:
 
Minimum of (Last dose date in AS0009 + 140^a) and (Date of last clinical contact^b) is \geq the date of the end of pandemic +1
 
Then the duration of exposure will be calculated as follows:
 
[Minimum of [(Last dose date in AS0009 – (date of the end of pandemic +1) + 140^a) + 1] and (Date of last clinical contact^b – (date of the end of pandemic +1) + 1)]
 
For subjects that died within 140 days following the last dose of BKZ this rule be adjusted to:
 
Date of death – (date of the end of pandemic +1) + 1

^a 140 days refer to 5 half-lives of BKZ.^b Date of last clinical contact for each subject is defined as the maximum of [last visit date including SFU visit, last AE start date (including imputed AE start dates), date of study termination or completion, last date of study drug administration following rules for partial treatment end dates as per Section 4.2.4].

BKZ=bimekizumab.

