1 INTRODUCTION

The purpose of this statistical analysis plan (SAP) is to provide all necessary information to perform the required statistical analysis for AS0009. It also defines the summary tables, figures, and listings to be generated in the clinical study report according to the protocol.

The SAP is based on the following study documents:

- Final protocol, 15 May 2017.
- Protocol Amendment 1, 17 July 2017.
- Protocol Amendment 2, 21 Mar 2018.
- Protocol Amendment 3, 06 Feb 2020.

The content of this SAP is compatible with the International Council for Harmonisation/ Food and Drug Administration E9 Guidance documents (1998).

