2 PROTOCOL SUMMARY

This is a Phase 2b, multicenter, 208-week, open-label extension (OLE) study to evaluate the long-term safety, tolerability, and efficacy of bimekizumab (also known as UCB4940), in up to 285 subjects with ankylosing spondylitis (AS). Only subjects who complete AS0008, a Phase 2b study, are eligible for enrollment into AS0009. At Week 48 of AS0008, all subjects continuing into AS0009 will undergo the final AS0008 study assessments and any non-overlapping AS0009 study entry assessments, and will then receive their first open-label dose (160mg every 4 weeks [Q4W] subcutaneously [sc]) of bimekizumab.

The study duration for each subject is up to a maximum of 224 weeks: an Open-Label Treatment Period of up to 204 weeks, followed by a Safety Follow-up (SFU) Visit 20 weeks after the last dose of bimekizumab.

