8.5 Impact of COVID-19

Additional sensitivity analyses as a result of the global COVID-19 pandemic are not anticipated as the onset of the pandemic was subsequent to all subjects completing Week 48 and therefore there is no impact on the analysis of the secondary efficacy endpoint.

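### The Prior and During pandemic TEAE rates in SAP 10.2.4 are confounded with AS0009 study week and attrition; a supplementary table by study-week band would separate them at small cost

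*SAP*

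**What the plan says.** SAP 10.2.4 gives the purpose of its extra outputs: "In order to assess the impact of the COVID-19 global pandemic on the primary safety endpoint of incidence of TEAEs and serious TEAEs". It then lists summaries with EAIR and EAER of "All TEAEs by time of onset relative to COVID-19 pandemic", and the same for serious TEAEs, in columns for before, during and (if applicable) after the pandemic.

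The cut is purely by calendar: "The date of 11 March 2020 is chosen as the date the World Health Organization declared COVID-19 as a pandemic". The denominator follows the same cut: "The time at risk will be calculated separately for each period in which the subject is counted". Under Table 10-5, Prior starts at the first AS0009 dose and applies to the whole Safety Set. During applies only to subjects still at risk on 11 March 2020. Neither 10.2.2 nor 10.2.4 stratifies or adjusts for study week.

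Two other places fix where study time can fall. SAP 8.5 says that "the onset of the pandemic was subsequent to all subjects completing Week 48". SAP Section 1 lists "Final protocol, 15 May 2017" as the earliest version of the protocol.

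**The concern.** Within each subject, Prior always comes before During. The two columns therefore differ in study week as well as in calendar time, and attrition adds to this because subjects who left early contribute only to Prior.

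The documents give several reasons why recorded AE rates could differ with study week even without a pandemic:

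- Site visits are 4-weekly to Week 12 and mostly 12-weekly afterwards (protocol Tables 5-1 and 5-2). At the home-dosing weeks, AEs are captured only if the subject chooses to come to the site (protocol 8.4 and 8.8).
- Subjects on 320mg at the end of AS0008 change to 160mg at AS0009 entry (SAP 3.7), so that transition is entirely in Prior.
- A completely unknown AE start date is set to the first AS0009 dose date unless the stop date is earlier (SAP 4.2.2), which places the event in Prior.
- Time at risk runs to 140 days after the last dose (SAP Table 10-2). For subjects who complete treatment, this off-drug stretch falls in During or Post.

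At stake is the reading of an analysis added for one purpose. A fall in rates with study week could look like a pandemic effect or cancel a real increase. The overall TEAE tables are not affected.

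**Working it through.** **The plan's own figure.** SAP Section 2 states: "The study duration for each subject is up to a maximum of 224 weeks: an Open-Label Treatment Period of up to 204 weeks", followed by the SFU visit 20 weeks after the last dose. 204 + 20 = 224 weeks, which agrees. SAP 10.2.4 itself gives no week boundaries.

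**Where study time can fall.**

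- Upper bound on Prior: 15 May 2017 to 11 March 2020 is 1031 days; 1031 / 7 = 147.3 weeks. No subject can have Prior time beyond about Week 147. First-dose dates are not in the documents, so this is only an upper bound. If first dosing followed "Protocol Amendment 1, 17 July 2017", it is 968 / 7 = 138.3 weeks.
- Lower bound on During: if every subject had passed Week 48, the last first dose was by about 10 April 2019 (11 March 2020 minus 48 weeks), so During holds essentially no time in Weeks 0-48. A late entrant who stopped before Week 48 is not strictly covered by the SAP 8.5 statement.
- Weeks 48 to 147 can occur in both periods. How much does depends on the unknown entry spread.

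**Person-time shares.** Assumptions: study week on 11 March 2020 is uniform over the window shown, follow-up is to Week 224, drop-out is 0% or 8% per year and unrelated to AE rate, and During runs to the end of follow-up (no Post column).

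| Study week at the cut | Prior time in Weeks 0-48 | Prior time in shared weeks | During time in shared weeks |
|---|---|---|---|
| 48-147 (widest possible) | 49-51% | 49-51% | 39-42% |
| 26-week entry spreads (48-74, 95-121, 121-147) | 36-80% | 9-21% | 8-16% |

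In the widest case, time after Week 147 is 58-61% of During. Over all the windows examined, mean study week is about 30 to 67 in Prior and 139 to 179 in During.

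**Crude ratio with no pandemic effect, step in rate.** Let *s* be the share of Prior time in Weeks 0-48, *r* the assumed rate per 100 patient-years there, and 100 the rate afterwards. During has no time in Weeks 0-48, so

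During/Prior EAER ratio = 100 / [100 + *s* (*r* - 100)].

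For example, *s* = 0.492 and *r* = 150 give 100 / (100 + 0.492 × 50) = 100 / 124.6 = 0.80.

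| Window | *s* (drop-out 0%, 8%) | *r* = 100 | *r* = 120 | *r* = 150 | *r* = 200 |
|---|---|---|---|---|---|
| 48-147 | 0.492, 0.513 | 1.00 | 0.91 | 0.80 | 0.66-0.67 |
| 60-120 | 0.533, 0.552 | 1.00 | 0.90 | 0.78-0.79 | 0.64-0.65 |
| 48-100 | 0.649, 0.663 | 1.00 | 0.88-0.89 | 0.75-0.76 | 0.60-0.61 |

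**Crude ratio with no pandemic effect, steady decline.** If the rate instead falls by 10%, 20% or 30% per year of study time, the crude ratio is about 0.80-0.81, 0.61-0.65 or 0.45-0.50 across the windows tried. If rates are flat it is exactly 1.00.

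**Same scenarios, stratified.** Comparing periods within 4-week study-week bands that both periods populate returns 0.998-1.000 in every case. This shows that banding removes the study-week component under these assumptions. It does not test for cohort differences, which the scenarios do not contain.

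**The case against.** The strongest reply is that these are descriptive supplements. SAP 10.2.4 specifies no rate ratio, test or attribution rule, and EAER has no confidence interval (SAP 10.2.2). Other outputs address the pandemic directly: a table and listing of COVID-19-related TEAEs, period flags in all AE listings, and summaries of affected visits (SAP 5.1.1). This stands, and it limits the point to a supplementary table and an interpretive statement. It does not remove the point, because the section gives assessing pandemic impact as its purpose and offers these columns for it.

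The second reply is that the gradient may be small. Subjects enter AS0009 after 36 or 48 weeks of bimekizumab (SAP 3.10), so an early on-drug AE peak would lie largely in AS0008, outside these tables. That also stands. The relevant axis is AS0009 study week, and a reader who inferred that Prior holds the start of drug exposure would be wrong. On AE capture, the 4-weekly spacing covers only the first 12 weeks and recurs between Weeks 204 and 208. The visit prompt also asks about health since the last visit (protocol 9.1.4), so wider spacing need not leave time uncovered.

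Third, banding has a cost beyond precision. Within a study-week band, Prior time comes mainly from early entrants and During time from later entrants, so entry-cohort differences replace part of the study-week difference. Amendment 2 of the SAP removed the by-region pandemic TEAE tables because events were few, and a finely banded table would meet the same problem. Both are real limits and belong in the text of the fix.

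**Conclusion.** The confounding is real and follows from the documents: Weeks 0-48 essentially only in Prior, time after at most about Week 147 only in During or Post, and those who left before the cut only in Prior. The crude contrast cannot by itself separate a pandemic effect from study week and attrition.

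A reader might go further and infer that the tables can never show a pandemic effect. The documents do not support that. The periods can share Weeks 48 to 147, and if rates are flat over AS0009 the crude ratio is unbiased. Nor should the ratios of about 0.60 to 0.91 be read as the expected bias. No passage gives a rate step or the entry dates, so the size, and whether there is any bias at all, is unknown. The figures show only that moderate gradients would be enough to mislead.

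This is an inexpensive improvement to a supplementary analysis. It does not call the primary safety summaries into question.

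**What to change.** In SAP 10.2.4:

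1. Keep the crude period columns, label them descriptive, and state that differences between them are not to be attributed to the pandemic, because the periods cover different AS0009 study weeks and different surviving subjects.
2. Add one supplementary table of EAIR and EAER for any TEAE and any serious TEAE (overall rows only) by pandemic period within bands of time since first AS0009 dose. Compare periods only in bands populated in both, from Week 48 to the largest study week reached before 11 March 2020. Use wide bands, show person-time in each cell, and apply the section's rule of separate time at risk to each period-by-band cell. Both sides of a band then consist of subjects still at risk at the same study week, which also deals with part of the attrition.
3. State the limits: few events and wide intervals in the shared weeks, possibly a small share of person-time if entry was quick (8-16% of During with a 26-week spread), and a comparison mainly of early with later entrants within each band.

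The cost is a short change of wording and one table. SAP 10.2.1 already derives time from the start of AS0009 study medication to each TEAE, and Table 10-5 already uses the dates needed for the denominators.
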